Analysis 1a identifies functional brain predictors of placebo analgesia. We focus on two systems related to placebo analgesia^{35, 409} (**Fig. 1a**): A **fronto-parietal system** involved in executive control and cognitive appraisal of emotion⁴²⁵⁻⁴³¹, and a **medial cortical-striatal-brainstem system**—including mid-lateral OFC, vmPFC, VS/nAC, and PAG. We hypothesize that behavioral analgesia will be related to anticipatory fronto-parietal activity and down-regulation of SIIPS responses (related to endogenous brain contributors to pain), but not modulation of the NPS (related to nociceptive pain), indicating that reported analgesia is influenced by decision bias and providing brain correlates of this bias.

Alternatively, analgesia may be correlated with NPS modulation and reductions in local targets of nociceptive afferents (S2, dpINS, mid-INS, aMCC), validating pain report as a predictor of neurobiological placebo effects. Increases in the medial system may also predict larger placebo effects on the NPS, linking this system to strong control of pain in placebo-responsive individuals.

Analysis 1b identifies structural brain predictors of placebo analgesia. We hypothesize that gray-matter density in the **medial cortical-striatal-brainstem system**, particularly nAC and vmPFC, will predict larger placebo responses in pain report, NPS, and SIIPS responses. Prior work suggests that gray-matter

| | Predictors | Outcomes: Placebo vs. control in |
|----|---|--|
| 1a | fMRI before, during pain, placebo vs. control | Placebo analgesia outcomes: 
 Pain report Pain-related fMRI 'signatures' (NPS, SIIPS) Separately for thermal, mechanical pain Separately for suggestion vs. conditioning Factor scores across these outcomes |
| 1b | Structural MRI | |
| 1c | Personality and behavior | |
| 2a | Twin status: Monozygotic vs. Dizygotic vs. unrelated Structural model | 
 Heritability of pain report, NPS, SIIPS Frontoparietal, Medial frontal-brainstem network increases |
| 2b | Twin status (mono/dizygotic) Genetic correlations | Heritability of correlations between placebo outcomes and predictors from Aim 1 |
| 2c | SNPs from candidate gene families | 
 Placebo outcomes Predictors from Aim 1 |
| 3a | Polygenic risk scores (PRS) in ENIGMA consortium | Regress placebo-linked structural features on SNPs in ENIGMA, yielding PRS. Test in Women's Health Initiative study. |

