Extensions and alternative plans. (1) We are developing new large-sample predictors of pain, and will test those as they become available. (2) Another important extension relates to individual differences in pain sensitivity. While not the main focus here, this dataset and our approaches are well-suited to predicting individual differences in pain sensitivity—a core feature of many pain conditions⁴⁴¹⁻⁴⁴³ and a risk factor for later chronic pain⁴⁴⁴⁻⁴⁴⁶. Models of risk for chronic pain following surgery (unfortunately common) and other procedures would be a crucial advance in precision medicine⁴⁴⁷⁻⁴⁵². Risks can be assessed at both phenotypic (predicted by evoked pain sensitivity) and genetic⁴⁵³ levels. Exploratory analysis will allow us to develop a foundation for understanding the neurobiology of individual differences in pain sensitivity.

Aim 2: Analyses 2a-2c will assess the heritability of placebo effects and placebo-predictive brain features, and relate these features to candidate gene families. **Analysis 2a (Aim 2.1)** identifies the heritability of placebo effects in pain report and brain responses for the first time. We hypothesize that heritability of pain reports will be modest, but heritability of placebo modulation of specific pain-related brain measures (the NPS and SIIPS) will be stronger, as these reflect component systems that are less etiologically complex and less context-sensitive than overall pain report. We also expect heritability to be high for gray-matter density in nAC and hippocampus⁴⁵⁴, and mPFC-brainstem pathways. The **model** for analysis 2a is a standard univariate ACE model^{455, 456}, which decomposes twin covariances for a trait of interest into additive genetic (A), shared environmental (C), and non-shared environmental (E) variance

components (Fig. 5). This model will be applied to individual placebo measures (e.g., thermal and mechanical pain), and also to latent variables (i.e., using a common factor model with thermal and mechanical pain loadings constrained to equality to identify the factor).

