Analysis 2b (Aim 2.2) identifies genetic correlations between placebo effects and brain features that predict them. It tests whether individuals who are more genetically related show higher cross-twin, cross-trait correlations. The model for this analysis is a bivariate extension of the ACE model^{455, 456} (Fig. 5b). The covariance between two measures is decomposed into genetic and environmental components with a Cholesky decomposition. The ACE variables for the first measure (e.g., placebo analgesia) are allowed to predict the second trait, and the second trait is allowed to have unique ACE influences. Of primary interest for **Aim 2.2** is the genetic correlation (rA) of the two phenotypes, which indicates the extent to which the genetic influences overlap across the two traits: $rA = a_{12}/\sqrt{a_{12}^2 + a_{22}}$; rC and rE can also be computed analogously. We will apply this model to relationships between analgesia and pain neurophysiology (i.e., NPS and SIIPS), and functional and structural features that predict placebo effects (e.g., nAC density, fronto-striatal activity). We expect the strongest genetic correlations in structural MRI measures that are likely highly genetically determined⁴⁵⁷. Structural features that are both placebo-linked and genetically associated with placebo (e.g., nAC gray-matter density) are good candidates for polygenic risk scores in Aim 3. **Power:** Assuming a moderate E variance of 30%, we will be able to detect genetic variance as low as 34% and shared environmental variance as low as 36% with >80% power. With an E variance of 40%, we can detect an A of 45% and C of 40% with >80% power. **Genetic correlations:** We will have power to detect either an rA or rC in the presence of an rE : Assuming 40% A and 30% C and E variances for both variables, we will be able to detect rAs of at least .36 and rEs as low as .22 with >80% power. Assuming 40% C and 30% A and E variances for both variables and correlations between both Cs and Es, we will be able to detect an rC of .34 and rE of .19 with >80% power.

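### Analysis 2a predicts that NPS and SIIPS placebo effects are more heritable than pain report, but no planned analysis tests that difference

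*Protocol*

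**What the plan says.** Protocol section IV, A.3, Analysis 2a (Aim 2.1) makes a comparative prediction. For pain report: "We hypothesize that heritability of pain reports will be modest". For the brain measures: "heritability of placebo modulation of specific pain-related brain measures (the NPS and SIIPS) will be stronger". The reason given is that the brain measures reflect simpler and less context-dependent systems.

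The model named "for analysis 2a is a standard univariate ACE model". On its scope: "This model will be applied to individual placebo measures (e.g., thermal and mechanical pain), and also to latent variables". The latent variable combines thermal and mechanical pain; it does not join pain report to a brain measure. Table 1 gives the 2a outcomes as "Heritability of pain report, NPS, SIIPS", with no contrast among them.

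Analysis 2b (Aim 2.2) extends the model to two traits and applies it to analgesia with NPS and with SIIPS. Its quantity of primary interest "is the genetic correlation (rA) of the two phenotypes, which indicates the extent to which the genetic influences overlap across the two traits"; rC and rE are to be computed in the same way. The power statements there concern one variance component of one trait, or a correlation. The SAP covers thermal pain ratings and does not mention heritability.

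**The concern.** Stronger than is a statement about a difference. Separate univariate fits give one A share per measure, each with its own uncertainty. They do not give the covariance between estimates that come from the same twins. No contrast, equality constraint, interval for a difference or decision rule is stated. A reader of the results would have only the ranking of the estimates, or the list of which A components were significant, and neither is a test of the difference.

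This is Aim 2.1's only directional prediction about placebo effects. With 300 pairs an A share is estimated imprecisely, so an apparent ordering can arise when nothing differs. This is separate from measurement reliability: it happens even if all three measures are equally reliable.

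**Working it through.** **Inputs from the documents.** 150 MZ and 150 DZ pairs (protocol section IV); 175 and 175 (section VII) as a sensitivity case; the power scenarios of Analysis 2b. **Assumed.** Alpha .05 for the ACE tests (the SAP gives it for pain ratings only); the true A and C shares outside those scenarios; cross-trait correlations of 0 or .3.

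**1. Reproduce the protocol's power.** With unit variance, the twin covariance is A + C for MZ pairs and A/2 + C for DZ pairs. The reduced model (CE to test A, AE to test C) is fitted by maximum likelihood to these population covariances. The minimized discrepancy is the noncentrality λ, and power = P(χ²₁(λ) > 3.841).

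| A / C / E | Component tested | λ | Power |
|---|---|---|---|
| .34 / .36 / .30 | A | 7.91 | 80.3% |
| .34 / .36 / .30 | C | 7.76 | 79.6% |
| .45 / .15 / .40 | A | 8.27 | 82.0% |
| .20 / .40 / .40 | C | 8.47 | 82.9% |

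The stated >80% is matched to within a point, so this twin model is a fair basis for what follows.

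**2. Separate fits when all three heritabilities are equal.** 1,500 simulated studies per scenario, 150 + 150 pairs, components bounded at zero. Each row shows one of the cross-trait correlations tried: .3 in the first row, 0 in the others.

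| A / C / E | Power for A | NPS above report | Both above report | NPS sig., report not | Both sig., report not |
|---|---|---|---|---|---|
| .45 / .15 / .40 | .83 | .48 | .33 | .14 | .11 |
| .40 / .30 / .30 | .89 | .51 | .34 | .10 | .09 |
| .30 / .30 / .40 | .53 | .51 | .33 | .25 | .13 |
| .40 / 0 / .60 | .50 | .51 | .36 | .26 | .13 |
| .30 / .10 / .60 | .34 | .48 | .30 | .21 | .06 |
| .20 / .10 / .70 | .15 | .48 | .30 | .13 | .02 |

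Simple arithmetic for independent traits agrees. With single-trait power p:

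- One given measure ranks above report half the time. Report is the lowest of three in 1/3.
- NPS significant, report not: p(1 − p). At p = .8 this is .16; the maximum is .25 at p = .5.
- Both significant, report not: p²(1 − p). At p = .8 this is .128; the maximum is 4/27 = .148 at p = 2/3.

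The SD of each estimated A is about .12-.15. For independent traits the SD of a difference is √2 times that, or .17-.21; simulated directly it is about .18-.21.

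**3. Power of a direct test.** Bivariate ACE, 1-df likelihood-ratio test that the two standardized A shares are equal, alpha .05. The ranges cover cross-trait correlations of 0 to .3.

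| Report A vs brain A | 150 + 150 | 175 + 175 |
|---|---|---|
| .30 vs .50 | 15-16% | 16-18% |
| .34 vs .54 | 17-18% | 19-21% |
| .20 vs .50 | 25-27% | 28-30% |
| .30 vs .60 | 28-31% | 31-35% |
| .20 vs .60 | 50-54% | 56-61% |
| .10 vs .60 | 56-61% | 63-67% |

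For .20 vs .50, a separate simulation gave 26% (C = .20) and 30% (C = .10). These correspond to λ = 1.73 and 2.06. At Holm's first step (alpha .025, critical value 5.024) the same λ give 18% and 21%. In simulations with equal A the joint test rejected in 2-5%.

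**The case against.** Four points on the other side are sound, and each limits what may be inferred.

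- **The protocol does not say the comparison will be read from rankings or significance labels.** It gives no rule at all. A reader might infer that a chance finding of this kind will be reported; the documents do not support that. The defect is that the prediction has no test.
- **A reader might infer that the planned models cannot address the difference.** That goes too far. The bivariate fits of Analysis 2b yield both A shares jointly for the relevant pairs, and univariate estimates could be compared by resampling pairs. No such comparison is planned, but little is missing.
- **A reader might infer that the predicted pattern often appears by chance.** That depends on the reading. The prediction concerns both brain measures, so the one-measure figure of about 50% is not the right headline. The relevant figures are 30-36% by ranking and about 2-15% by the strictest significance pattern.
- **A reader might infer that later aims rest on this ranking.** They do not. Aim 3 carries forward structural features chosen by their genetic correlation with placebo response.

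It can also be said that a direct test would usually be inconclusive. That is true, but it favours reporting the difference with its interval: separate fits alongside a >80% power statement do not show the reader how little this sample can resolve.

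**Conclusion.** The point holds in a limited form. Analysis 2a predicts a difference in heritability, and no analysis in the protocol or SAP tests it, although a suitable model is already planned for the same trait pairs. Under equal heritabilities with 150 + 150 pairs, the predicted ordering of both brain measures arises in about 30-36% of studies. NPS significant with report not arises in about 14-16% at the protocol's own 80%-power points and in up to about 25% at lower single-trait power. Both significant with report not arises in about 2-15%.

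The sizes rest on assumed variance shares and cross-trait correlations, because the documents give no expected heritability for any of the three measures. Section VII's larger sample raises power only slightly: no gap tried reached 80% at either size. The change is worth making, but it concerns one hypothesis of Aim 2.1; the SAP's main analysis and Aim 3 are unaffected.

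**What to change.** 1. In the bivariate ACE models already planned for analgesia with NPS and analgesia with SIIPS, add a 1-df likelihood-ratio test that the two standardized A shares are equal. Apply Holm across the two tests.
2. Report each difference in A share with a 95% confidence interval.
3. Claim that a brain measure is more heritable only where the Holm-adjusted test supports it. Otherwise report the ordering as unresolved.
4. State that power for this comparison is low: about 15-60% at alpha .05 over assumed gaps of .20 to .50, and for .20 vs .50 about 26-30%, or about 18-21% at Holm's first step. Say that the >80% figures in Analysis 2b do not apply to it.
5. Do not use the difference in MZ correlations as evidence on heritability. Under the ACE model it is a difference in A + C and could be entirely shared environment.

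The cost is a few lines of text and one extra constrained fit per trait pair, with no new data. The downside is that the claim becomes harder to make.

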In **Analysis 2c**, we will attempt to replicate previously identified associations between candidate genes and placebo effects (reviewed in ³⁷⁶). We expect the most meaningful results to come from polygenic risk scores (see below), but it is important for the field to know whether the candidate genes already identified predict placebo responses or not. Based on previously reported associations, our study is well powered to determine this. We focus on SNPs within (+/- 10 kb of gene boundaries) several neurotransmitter/ neuropeptide gene families previously linked with placebo analgesia in pharmacological and molecular imaging studies, including **catecholamine and monoamine clearance** (COMT, MAO-A), **opioids** (OPRD1, OPRM1, OPCML, SIGMAR1, OPRK1, PDYN, OGFR), **dopamine** (DBH, DRD5, PPP1R1B, DRD1, SLC6A3, DRD4, DRD2, DRD3, CALY), **serotonin** (5-HT; HTR[1-3]A/B, HTR[1-3]B, HTR1[D-F], HTR2C, HTR3C/D/E, HTR5A/B, HTR[4, 6, 7], MAOA, SLC6A4), **cannabinoids** (CNR1, CNR2, CNRIP1), and **cholecystokinin** (CCK; CCKAR, CCKBR, CCK, DBI), and BDNF. We will test for statistical enrichment in SNP associations within these gene families using the MAGMA

[figure not shown]
[figure not shown]

Figure 5. Structural ACE model for heritability. Circles: latent variables for the genetic (A), shared environmental (C), and unique environmental (E) influences for each twin in a pair. MZ: monozygotic; DZ, dizygotic. The correlation between the genetic effects (A) is set to 1.0 in MZ twins and 0.5 for DZ twins (who share on average half their segregating genes). All twins are reared together in our sample, so C is set to 1.0 in both groups, and E is set to zero because unique influences are unshared, by definition. Right: Bivariate extension for estimating genetic correlations. nAC: nucleus accumbens, an example candidate region.

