[doi:10.1371/journal.pcbi.1004219] and VEGAS [http://dx.doi.org/10.1016/j.ajhg.2010.06.009] software tools. This set comprises 48 genes with an estimated 320 genotyped SNPs and 4800 imputed SNPs with MAF > .005. Most of these SNPs do not exist on the Affymetrix Axiom Precision Medicine chip, but they can be imputed with excellent fidelity from genotyped SNPs using the Haplotype Reference Consortium reference sequence database [doi:10.1038/ng.3643], which has replaced the 1kG reference database as the gold standard. This approach is now standard for GWAS. We estimate imputation of ~97% of candidate SNPs with ~99% accuracy using the *MACH* program⁴⁵⁸. **Power:** Assuming correction across ~50 candidate genes, we will have 80% power to detect effects of $d = 0.24$ ("small") or greater, substantially smaller than most previously reported associations. **Hypotheses:** Previous studies reported that opioid genes were related to fMRI signal in PAG and vmPFC⁴⁵⁹⁻⁴⁶¹; dopamine genes to enhanced placebo after conditioning, compared to suggestion alone^{462, 463}; and serotonin and CCK genes to (a) anticipatory activity in vmPFC, which correlates negatively with placebo analgesia^{63, 70, 464} and positively with anxiety⁴⁰⁸, and (b) activity in the serotonergic dorsal raphe nucleus (adjacent to the PAG), which is activated in placebo studies^{162, 403, 465, 466} and is linked to threat and analgesia in animal models⁴⁶⁷⁻⁴⁶⁹.

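### Analysis 2c is described as replication of reported candidate-gene associations, but its only assigned test is gene-family enrichment, which cannot show that a reported allele effect recurs and, when null, cannot refute it

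*Protocol*

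**What the plan says.** Protocol section IV, A.3, Aim 2, Analysis 2c gives the purpose: "we will attempt to replicate previously identified associations between candidate genes and placebo effects". It adds that "it is important for the field to know whether the candidate genes already identified predict placebo responses or not", and then: "Based on previously reported associations, our study is well powered to determine this".

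The SNP scope is broad: "We focus on SNPs within (+/- 10 kb of gene boundaries) several neurotransmitter/ neuropeptide gene families". The assigned test is: "We will test for statistical enrichment in SNP associations within these gene families using the MAGMA" and VEGAS software. The size of the set is given as: "This set comprises 48 genes with an estimated 320 genotyped SNPs and 4800 imputed SNPs with MAF > .005". The power sentence assumes correction over about 50 genes and claims 80% power at d = 0.24. It compares that effect with those in earlier reports.

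For 2c the protocol names no reported variant, effect allele, allele direction or replication criterion. The hypotheses at the end of 2c link whole gene families to outcomes, mostly brain regions. Table 1 lists the 2c predictor only as SNPs from the candidate families. The SAP contains no genetic analysis.

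**The concern.** The purpose and the test do not match. To replicate a reported association at allele level, one tests the reported variant, on the reported outcome, in the reported direction. An enrichment statistic pools evidence over many SNPs and, as is usual for such tests, ignores sign; that is a general property, not something the documents state. Two consequences follow.

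- A different SNP in a listed gene, or the reported SNP acting in the opposite direction, could produce a positive result that is then described as replication.
- A true effect at the reported SNP is spread over its neighbours and can be missed, so a null could be read as refutation.

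The protocol wants to learn whether the candidate genes predict placebo response or not, so the negative arm of that question matters as much as the positive one.

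**Working it through.** **Inputs.** From Analysis 2c: 48 genes, 4800 imputed SNPs, correction over about 50 genes, d = 0.24, 80% power. From the sample description in section IV: N = 600. Assumed: family-wise alpha .05 two-sided (the SAP gives .05 for its main analysis only), two equal genotype groups, twins treated as independent, and a gene test that sums chi-squares (the protocol names only the software).

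**SNPs per gene.** 4800/48 = 100 on average.

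**The plan's own figure.** Alpha = .05/50 = .001, so z = 3.2905 + 0.8416 = 4.132. With 600 people in two equal groups, the detectable d = 2 × 4.132/√600 = 0.337 two-sided (0.321 one-sided). The stated 0.24 is not reproduced on this basis. It appears with 600 per group (4.132 × √(2/600) = 0.239) or with a one-sample formula at n = 300 (4.132/√300 = 0.239). That mismatch is a separate matter. What counts here is that 0.24 is a single-effect calculation on either route, not power for an enrichment test.

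**Dilution at matched alpha.** Fix the effect at 80% power for its SNP alone, two-sided .001: λ = 4.132² = 17.07, which is d of about 0.34 at N = 600. If the gene holds m effectively independent SNPs and only one carries signal, power = P[χ²(m, λ) > χ²₀.₉₉₉(m)].

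| m (assumed) | Critical value | Power of pooled test |
|---|---|---|
| 1 | 10.83 | 80% |
| 5 | 20.52 | 53% |
| 10 | 29.59 | 36% |
| 20 | 45.31 | 20% |

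A one-sided test of the listed SNP at the same .001 has power Φ(4.132 − 3.090) = 85%.

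**Direction.** In a simulation with 100 SNPs per gene, one causal SNP and assumed linkage disequilibrium (AR(1) correlation 0.7 to 0.95, in blocks of 20 to 100 SNPs), the pooled test at d = 0.34 rejected 12% to 45% of the time. The rate was essentially the same whether the allele acted as reported or in reverse. A one-sided test of the reported allele rejected about 86% of the time in the reported direction and 0% in the opposite one. At d = 0.24 the pooled test had about 2% to 14% power, against 36% for a two-sided test of the SNP alone at .001.

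**What a list achieves at the protocol's own effect size.** At d = 0.24 the expected z is 0.24 × √600/2 = 2.94. For a one-sided test at .05/k, power = Φ(2.94 − z₁₋.₀₅/ₖ):

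| List length k (assumed) | Alpha | Power |
|---|---|---|
| 5 | .01 | 73% |
| 10 | .005 | 64% |
| 20 | .0025 | 55% |

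Holm is at least as powerful as this fixed .05/k.

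**The case against.** The strongest reply is that the protocol words its question about genes, not alleles. A reader might infer that neither a positive nor a negative enrichment result answers the question asked. The documents do not support that for the positive arm: a positive gene or family result does bear on whether the candidate genes predict placebo response. The gap is that it does not establish recurrence of a reported allele effect, and that a null does not refute one.

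A reader might also infer that outcomes are unspecified and that no SNP-level test exists. Neither is quite so. The 2c hypotheses link opioid, dopamine, serotonin and CCK genes to particular responses. The statistical learning framework in A.4 plans a permutation test of SNP importance, with feature selection on six gene families. The fourth extension under Aim 3 adds SNP tests in the same families. But none of these is assigned to 2c as a replication test of a named variant and direction, so they soften the point without removing it.

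A third tempting reading is that a prespecified list would bring power to 91% to 96%. At λ = 17.07, lists of 20, 10 and 5 do give 91%, 94% and 96% one-sided. Set beside a pooled test at .001, however, that mixes removal of dilution with a looser alpha and one-sidedness. At matched .001 the figure is 85%, and the effect itself is larger than the protocol's d = 0.24.

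Two further points stand. The families were chosen partly from pharmacological and imaging evidence, so some genes may have no reported allele and can only be covered by enrichment. And the protocol itself expects its polygenic scores to be more informative than 2c.

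**Conclusion.** The concern holds as a mismatch between stated purpose and assigned test in a secondary analysis. Followed as written, 2c could present enrichment from another SNP or an opposite effect as replication, and could miss a reported effect that is real.

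The size is illustrative: 80% power falls to 53%, 36% or 20% with 5, 10 or 20 effectively independent SNPs per gene, against 85% for a direct one-sided test at the same alpha. These figures rest on the assumed number of independent SNPs, a sum-of-chi-square statistic, one causal variant, equal genotype groups and independent subjects. The missing variant list and direction depend on none of those assumptions.

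Direct testing is the better-aimed analysis, but at d = 0.24 it is not strong enough for a null to settle the matter.

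**What to change.** Before any genotype–outcome analysis:

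- List each reported SNP with its placebo outcome and effect-allele direction, taken from the review that Analysis 2c cites.
- Make direct tests of that list the replication analysis, Holm-corrected over the list and with twin covariance in the model. State the sidedness.
- Count replication only when the effect lies in the reported direction. Report two-sided estimates and confidence intervals, so that opposite effects are visible and a null is read by what the interval excludes.
- Keep MAGMA/VEGAS enrichment as a secondary gene-family analysis, including for genes with no reported allele, with its own power statement. Do not describe it as replication.

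The cost is compiling a list and adding SAP text; no new genotyping is needed. The downside is that poorly imputed reported SNPs must be declared untestable (the protocol expects about 97% of candidate SNPs to be imputed), and genes without a reported variant are covered by enrichment alone.
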